6.2.2 Study visit 2: Hyperinsulinemic, euglycemic clamp

Study subjects will undergo a two-step clamp as depicted in **figure 2**.

Min -150		60 -3 	0 0) 12	20 15	50 2	70 30	00 330			
	Equilibration	Control	Bx #1	Period 1	Sample 1	Period 2	Sample 2	Bx #2			
Γ				6,6- ² H Glucose							
				Perip. Insulin 12 mU/m²/m (3x basal)	in	Perip. Insulin 40 mU/n (10x basal)	n²/min				
				Basa	l Glucag	on 0.65 ng/kg/min					
	Somatostatin 60 ng/kg/min										
				Peripheral Glucose to maintain plasma glucose at 90 mg/dL							

Figure 2: Hyperinsulinemic, euglycemic clamp protocol. Insulin infusion rates are predicted to cause a 3 and 10-fold rise in plasma insulin levels in control subjects. In a 70 kg, 1.73 m² individual, 12 mU/m²/min would approximately equal 0.3 mU/kg/min and 40 mU/m²/min would approximately equal 1.0 mU/kg/min.

6.2.2.1 Overnight CRC stay

Subjects will be admitted to the Vanderbilt CRC on the night before the study and begin fasting except for water at 10 PM. All female subjects will have a second hCG measured to confirm the absence of pregnancy upon arrival to the CRC.

T1DM and MODY2 subjects will then be given a continuous IV infusion of regular human insulin (recombinant DNA origin), titrated by the protocol of White et al. (49) as shown in **Table 3**.

Glucose reading (mg/dL)	Insulin Infusion rate (U/h)
above 250	5
201-250	4
171-200	3
141-170	2
121-140	1.5
101-120	1
81-100	0.8
61-80	0.5
under 60	0

Table 3: Algorithm for Maintenance of OvernightEuglycemia

Glucose will be checked on an hourly basis using a calibrated, hospital bedside glucose monitor. Testing this protocol in 25 subjects with T1DM, White et al. reached and maintained near-euglycemia (101 ± 2) mg/dL) in the fasted state. Glucose fell to below 60 mg/dL on six occasions and to below 50 mg/dL on only one occasion. T1DM and MODY2 study patients should be at euglycemia when the clamp study begins (matching them with non-diabetic controls) and the overnight-titrated fasting insulin infusion rate should approximate the peripheral insulin infusion rate needed for euglycemia in each patient. Should glucose fall to < 75 mg/dL the PI may elect to infuse a small dose of 20% dextrose to prevent hypoglycemia. Should glucose fall to < 55 mg/dL and the patient experience symptoms of hypoglycemia, 20% dextrose will be at bedside to treat the hypoglycemia (e.g. 75 mL of 20% dextrose delivers 15 gm of glucose). If glucose were to fall to < 55 mg/dL, the following morning's clamp study would need to be postponed to a later date

because of the confounding influence of the counterregulatory response to hypoglycemia.

The PI will be physically present in the CRC for at least the first 3 overnight insulin infusions (T1DM or MODY2 subjects) to monitor and adjust the insulin infusion from the protocol if needed. Thereafter, the PI and CRC nurse manager will confer on the need for the PI (or a qualified M.D., N.P., or P.A.) to be physically present for the overnight insulin infusions based on the safety profile of the preceding IV insulin infusions. If the PI is not physically present, he will be readily available via telephone pager and will be within 20 minutes of the CRC.

Control subjects will be admitted on the night prior to the study, begin fasting at 10 PM, but no insulin will be infused until the start of period 1.

6.2.2.2 Hyperinsulinemic, euglycemic clamp

As depicted in figure 2, each experiment will consist of:

- 1. a 90 min equilibration period for [6,6-²H]glucose,
- 2. a 30 min basal sampling period (control),
- 3. a 30 min period to obtain muscle biopsy (Bx) #1; then
- 4. 2 consecutive, 150 min experimental periods where increasing IV infusions of regular human insulin are given, and
- 5. a 30 min period for Bx #2.

Somatostatin will be infused into a peripheral vein to allow for a pancreatic clamp. Simultaneously glucagon will be infused into a peripheral vein at a rate chosen to approximate basal concentrations of glucagon at the liver, preventing a fall in glucagon that would otherwise occur secondary to the hyperinsulinemia and somatostatin. As noted previously, this allows for insulin and glucagon concentrations to be identical between test subjects, enabling a direct assessment of hepatic insulin sensitivity (50). In the United States, numerous groups currently use somatostatin for the purpose of "clamping" pancreatic hormone secretion (30-36) and it is used extensively in Europe for the same purpose (37-41). Plasma glucose will be monitored every 10-30 minutes during the equilibration, control, and Bx1 periods, then every 5-10 minutes during the 2 consecutive 150 min experimental periods and Bx2. The YSI Glucose Analyzer (Yellow Springs, OH), the gold standard instrument for glucose concentration analysis, will be used during the clamp study. IV glucose will be infused to maintain plasma glucose at approximately 90-100 mg/dL throughout the study. At nine points in the study (3 times each during the control, sample 1, and sample 2 periods as in figure 2), a larger blood draw will be made from a second intravenous catheter to determine plasma concentrations of the following:

- 6,6 2H-glucose
- Insulin
- Catecholamines
- Glucagon
- Cortisol
- C-peptide
- Free Fatty Acids
- Lactate, glycerol, alanine (and possibly betahydroxybutyrate)
- Triglycerides

These blood draws are calculated to equal just under 160 mL in total blood volume. This includes the volume of blood that is wasted to clear the IV line with each blood draw.

6.2.2.3 Muscle biopsy

Subjects will be asked to allow the study team to perform two muscle biopsies during the study. If the subjects decline the muscle biopsy, they will still be allowed to participate in the hyperinsulinemic, euglycemic clamp.

The muscle biopsies, Bx #1 and #2, will be obtained immediately before study period 1 and immediately following study period 2, respectively (figure 2). Percutaneous biopsies will be performed on the lateral portion of the quadriceps femoris muscle (vastus lateralis) using sterile technique. A minimum distance of 2 cm proximal or distal between the two sampling sites will be used to minimize specimen artifact caused by trauma, inflammation, and/or scarring. Local anesthesia with lidocaine 0.5-1% will be applied in two steps: first within the dermis and second into the muscle fascia before the biopsy is obtained. A 4-6 mm

incision through the skin will be made with a scalpel. Then we will insert a trocar into the incision site, pushing through the muscle fascia, and advance to ensure that the cutting chamber lies fully within the muscle. We will apply suction to withdraw the muscle tissue into the cutting chamber and then we will rotate the trocar clockwise 90 degrees to maximize the amount of muscle sample obtained. We will place sterile gauze and apply pressure with a cold compress for 10 minutes to minimize bleeding, inflammation, and pain. During and after the procedure, participants will be allowed to take acetaminophen on an as needed basis to minimize pain under the supervision of the PI. Muscle samples will be immediately blotted free of visible non-muscle tissue, flash frozen in liquid nitrogen and stored at -80°C until analysis. Samples will be analyzed using immunoprecipitation/immunoblot analysis.

6.2.2.4 Completion of clamp study

Upon completion of the study, insulin will be discontinued and the study subject will be allowed to eat. Plasma glucose will be monitored every ten minutes for an additional hour and the glucose infusion rate will be steadily decreased to maintain glucose > 120 mg/dL. Patients taking insulin at home will be instructed to resume their home regimen, however they will be instructed to check glucose before dinner, bedtime, and at 2 AM following the study. These glucose readings will be recorded on a 24-hour poststudy glucose log (see appendix). If glucose is < 120at any of these checks, they will consume an additional 15-30 gm of glucose with 5-15 gm of protein to prevent hypoglycemia. As an example one Luna bar has 26 gm of carbohydrates and 9 grams of protein. By the following morning, risk of hypoglycemia as a result of participating in the clamp study will be no greater than their baseline risk.

After local anesthesia from the muscle biopsy wears off, the subject may experience soreness for less than a week; during this time the study team will recommend subjects use acetaminophen 650 mg every four hours as needed for pain or discomfort, with no more than 2,000 mg in a 24 hour period. The study team will instruct the participants and parents of adolescent participants on post-procedural wound

management. We will recommend that subjects minimize walking on the day of discharge from the study; activity should gradually be resumed following the procedure. Vigorous activity or sport should be avoided for the first few days and resumed cautiously as discomfort subsides. In addition to contacting the subject's family on the day following the study to review blood glucose numbers, the study team will check on the status of wound healing during the call on the day following the study as well as 5-7 days after the study. The subject will be instructed to notify their primary care physician if they have marked swelling and discomfort of the whole muscle (beyond the anticipated bruising); if the biopsy site is painful more than a week after the biopsy was taken; if the biopsy site appears swollen, purulent, or fluctuant; if there is persistent oozing from the biopsy site; or if a temperature of >= 102 degrees F develops.

6.2.2.5 Rescheduling clamp study after a technical issue

It is possible once a clamp visit has begun a technical issue will prevent the successful completion of the study. For example, IV access may be lost during the study or otherwise uneventful hypoglycemia (glucose < 55 mg/dL) may occur for those participants receiving an overnight IV insulin infusion (section 6.2.2.1). In the event such a technical issue occurs, the PI may elect to reschedule a repeat clamp study with the following stipulations:

- A) The PI deems the technical issue poses no serious danger to the participant were it to occur again and the participant wishes to repeat the study
- B) The rescheduled clamp occurs within six months of the original screening visit
- C) An abbreviated screening procedure has been completed within one month of the repeated clamp visit. This abbreviated screening will re-assess inclusion/exclusion criteria (table 2) and safety to be restudied. The abbreviated screening will include:
 - Fasting blood tests: a complete metabolic panel (screening for hepatorenal disease), hemoglobin (screening for anemia), c-peptide, insulin, HbA1c, lipid panel
 - Urine pregnancy testing: on the night prior to the clamp in females

 History and Physical Exam: the participant's interval clinical history will be reviewed by the PI (or a designated KSP who is an M.D., Nurse Practitioner, or Physician's Assistant) on the evening prior to the clamp study and a physical exam will be performed. Anthropometric measurements will be repeated with the assistance of CRC staff or KSP.

7.0 Risks

During the participant consent/assent process study personnel will address potential discomfort and risks associated with the study protocol. These will be included in the consent/assent form.

The following risks associated with participation in this study are perceived as low:

- venipuncture and intravenous angiocatheter placement: possible hematoma, site infection, nausea, and vasovagal syncope. These risks will be minimized by performing the procedure with the subject seated and cleaning the site with the appropriate antiseptic prior to breaking the skin.
- DEXA scan: studies of the radiation dose to patients from a total body DEXA scan have confirmed that patient radiation exposure is small compared to many other sources of exposure. For the total body fast scan mode that will be employed the average skin entrance dose is 0.2 μ Sv (51, 52). By comparison a chest x-ray is associated with a patient dose of 50 μ Sv.

The following risks associated with participation are additionally considered:

7.1 Exercise testing

During the screening visit, subjects will perform an exercise test to measure VO₂ max. Because inclusion/exclusion criteria dictate that the subjects will be young (ages 13-35), not obese (BMI 20-28), and those patients with diabetes will have relatively ideal glycemic control (HbA1c 6.0-8.0%), the risk of a cardiovascular complication of exercise is considered to be low. The greatest risk of the exercise test is hypoglycemia in the T1DM patients who will have been fasting overnight. The patient will be asked to check their capillary glucose using their home meter immediately prior to exercise and if glucose is < 100 mg/dL, they will consume 15 gm of glucose immediately prior to the \sim 10 minute exercise test. Immediately following this, all subjects will be provided with a meal, further minimizing exposure to hypoglycemia subsequent to the brief exercise test.

7.2 Hyperinsulinemia

Subjects will be exposed to hyperinsulinemia during the clamp study, which could lead to hypoglycemia and hypokalemia. We will implement the following to minimize these risks:

- As shown in figure 2, the highest insulin rate used will be 40 mU/m²/min. This is the most frequently applied insulin infusion rate in human hyperinsulinemic, euglycemic clamp studies.(53) This infusion rate is anticipated to result in plasma insulin concentrations between 50 and 130 μ U/mL, (54) levels that are within the range of physiological hyperinsulinemia and comparable to concentrations seen after meal ingestion. (53, 55, 56) By comparison, the most commonly used insulin infusion rate in the treatment of diabetic ketoacidosis is 0.1 U/kg/hr.(57) In a 70 kg, 1.73 m² individual, this infusion rate would equal 67 mU/m²/min, over 50% higher than the 40 mU/m²/min rate used in this study.
- Glucose will be monitored every hour during the overnight basal insulin infusion as outlined in 6.2.2.1. Glucose will be monitored every 5-10 minutes throughout the hyperinsulinemic clamp to guide the variable dextrose infusion and ensure euglycemia. Because glucose is monitored so frequently, a trend toward hypoglycemia would most likely be detected before hypoglycemia actually occurred. If hypoglycemia did occur, however, this frequent monitoring would allow for rapid detection of the low glucose concentration and rapid corrective treatment with an infusion of IV glucose (dextrose).
- Concentrated dextrose will be at bedside to treat iatrogenic hypoglycemia. If hypoglycemia occurred it could rapidly be corrected.
 For example, a 75 mL IV bolus of 20% dextrose (15 gm of glucose) would be expected to bring glucose up above the hypoglycemic range in less than 5 minutes. This dextrose could be given into either of the two IV angiocatheters available during the study.
- A licensed MD, NP, or PA will be on call throughout overnight CRC stay and bedside during clamp procedure
- Potassium will be monitored using bedside istat monitor (and oral potassium replacement will be given as needed)
- Glucose will continue to be monitored following the study for at least 1 hour
- Patients will be required to consume mixed meal immediately following clamp procedure. T1DM subjects will not be discharged unless blood glucose > 120.
- Vital signs will be monitored throughout clamp procedure
- Subjects will be counseled on the risk of late hypoglycemia the evening and night following the clamp. They will be advised of the importance of checking their blood glucose at bedtime and during the night to maintain a minimum of 120 mg/dL

7.3 Muscle biopsy

Having a muscle biopsy may cause pain, soreness, bruising, or infection at the biopsy site. Every effort will be made to prevent or minimize these side effects of the muscle biopsy:

- the biopsy will be of a large muscle that is easily identified on physical exam: the vastus lateralus of each lower extremity
- sterile technique will be used to minimize risk of infection
- local anesthesia with lidocaine (0.5-1.0%) will be used prior to the incision
- after local anesthesia wears off, the subject may experience soreness for less than a week; during this time the study team will recommend subjects use acetaminophen 650 mg every four hours as needed for pain or discomfort, with no more than 2,000 mg in a 24 hour period.
- the study team will recommend that subjects minimize walking on the day of discharge from the study; activity should gradually be resumed following the procedure. Vigorous activity or sport should be avoided for the first few days and resumed cautiously as discomfort subsides.
- The subject will be instructed to notify their primary care physician if they have marked swelling and discomfort of the whole muscle (beyond the anticipated bruising); if the biopsy site is painful more than a week after the biopsy was taken; if the biopsy site appears swollen, purulent, or fluctuant; if there is persistent oozing from the biopsy site; or if a temperature of >= 102 degrees F develops.

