6.2 Study visits: Each subject will participate in two study visits.

6.2.1 Study visit 1: Initial screening

All subjects will be asked to arrive at the CRC at 8 AM on the morning of study visit 1. Participants will be asked to begin fasting except for water 8 hours before the visit. T1DM subjects will be instructed beforehand that if they have hypoglycemia during the overnight fast to use the commonly known "Rule of 15" with glucose tablets

(http://www.joslin.org/info/how to treat a low blood glucose.ht ml) to correct their hypoglycemia.

Upon arrival, the following will take place:

 Consent/Assent: The PI or designated Key Study Personnel will obtain consent/assent from all participants.
 Consent/assent will be obtained in a private room in the CRC prior to beginning study procedures. The consent and assent form will be provided to the subject and family (if applicable) for review prior to the visit. The PI or designated Key Study Personnel will review the consent/assent forms with the family in detail and provide time for questions to be answered. A copy of the consent/assent form will be provided.

- History and Physical Exam: Each subject's clinical history will be reviewed by the PI (or a designated KSP who is an M.D., Nurse Practitioner, or Physician's Assistant) and a physical exam will be performed. Anthropometric measurements will be taken with the assistance of CRC staff or KSP. If at this point the subject continues to meet inclusion and criteria (table 2), he or she will proceed with the remainder of visit 1.
- Resting Metabolic Rate (RMR): Resting metabolic rate (RMR) will be measured using indirect calorimetry (45).
 Subjects will recline in a hospital bed during this test. When the rate of oxygen consumption changes by less than 2% over a five minute period, it will indicate that the RMR has been achieved.
- Blood and urine tests: each subject will have labs drawn following their 8-hour overnight fast. These include a complete metabolic panel (screening for hepatorenal disease), hemoglobin (screening for anemia), c-peptide, insulin, HbA1c, lipid panel, and urine pregnancy test (for females).
- DEXA: Lean body and fat mass will be measured using dualenergy X-ray absorptiometry (DXA) (Lunar Prodigy, enCore software version 10.5, GE Medical Systems).

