- Peripheral artery tonometry: Reactive hyperemiaperiopheral artery tonometry (RH-PAT) endothelial function testing will be used (Endo-PAT, Itamar Medical Ltd.) to assess risk of endothelial dysfunction and future premature cardiovascular disease. The subject will sit in a reclining chair with the hands at heart level and propped in a comfortable position such that the fingers are hanging freely. Fingertip probes are placed on both index fingers and pulse wave amplitudes are recorded for the duration of the study. After 5 min of baseline measurement, arterial flow to the nondominant arm is occluded for 5 min using a BP cuff inflated to 40 mmHg above systolic pressure. After the 5-min occlusion, the cuff is rapidly deflated to allow for reactive or flowmediated hyperemia. Pulse wave amplitudes are recorded for at least 5 min after the cuff is deflated. An integrated software program compares the ratio of arterial pressure in the two fingers before and after the occlusion to calculate the RH-PAT score.(46)

- VO₂ max Testing: Exercise testing will be performed to assess VO₂ max. The Bruce protocol will be used, as described elsewhere (47). Participants will be asked to perform a progressive treadmill test for about 10 minutes (or until fatigued). Attainment of a valid measure for VO₂ max will be if two of the following three criteria are met: 1) a respiratory exchange ratio of 1.1 or greater, 2) attainment of a maximal measured heart rate within 10 beats/ min of the age predicted maximum (220-age), or 3) no change in oxygen consumption despite an increase in work load. T1DM participants will check their blood glucose prior to exercising. If glucose is < 120 mg/dL, a 15-30 gm carbohydrate snack will be provided.

Following VO₂ max testing, the subject will be provided with a meal from the CRC kitchen. T1DM subjects will be instructed to resume their routine insulin regimen. Patients will then be discharged home. Once the data is collected from the screening visit and inclusion/exclusion criteria are confirmed as being met, the subject will be contacted. Study visit 2 will be scheduled within one month of study visit 1.

Premenopausal females will be scheduled for their study during the follicular phase of their menstrual cycle (day 2-10) to reduce a potential confounder of insulin sensitivity.(48)

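### Sections 6.2.1 and 7.1 set different pre-exercise carbohydrate rules for the same VO2 max test in fasted T1DM subjects (below 120 versus below 100 mg/dL), and neither is said to govern.

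*Combined protocol and SAP*

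**What the plan says.** Section 6.2.1 describes the screening visit. On fasting it says: "Participants will be asked to begin fasting except for water 8 hours before the visit". The VO2 max test comes late in that visit, and the meal comes after it. T1DM subjects check their glucose before exercising, and the rule is: "If glucose is < 120 mg/dL, a 15-30 gm carbohydrate snack will be provided".

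Section 7.1 discusses the risks of the same screening test. It states: "The greatest risk of the exercise test is hypoglycemia in the T1DM patients who will have been fasting overnight". T1DM subjects are to take a capillary reading on their home meter immediately before exercise, and "if glucose is < 100 mg/dL, they will consume 15 gm of glucose immediately prior".

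Section 7.1 also explains why cardiovascular risk is thought to be low. It says that "inclusion/exclusion criteria dictate that the subjects will be young (ages 13-35" years), and it adds a BMI range of 20-28 and an HbA1c range of 6.0-8.0%. Section 7.6.1 likewise describes the young adults with diabetes as aged 18-35. Table 2 in section 4.0 admits T1DM and MODY2 subjects aged 13-51 and controls aged 18-51.

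**The concern.** Two sections give different instructions for one test in one group of subjects. Neither refers to the other, and the protocol states no order of precedence. The difference bears on the hazard that section 7.1 itself ranks first for this test, and section 7.1 carries the lower trigger and the smaller amount. A fasted T1DM subject reading 110 mg/dL would be given carbohydrate by staff working from section 6.2.1. Staff working from section 7.1 would have no instruction to give any.

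Section 7 is not idle text. Its opening says that study personnel will go over the risks at consent and assent and that the forms will include them. Section 8.0 reports hypoglycemia as an adverse event only when a subject needs help because of loss of consciousness. A milder low during or after exercise would therefore not show up in adverse event reports as a sign that the wrong rule was in use.

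The secondary issue is that the written case for low cardiovascular risk during exercise rests on an age range that stops at 35, while enrolment runs to 51. The text gives no rationale for ages 36-51.

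**Working it through.** No stated figure needs to be reproduced. The check is a side-by-side reading of the two rules.

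**Same test and same subjects.** Section 6.2.1 places the VO2 max test at study visit 1, the initial screening, after an 8-hour fast. Section 7.1 refers to the VO2 max test at the screening visit in T1DM patients who have fasted overnight. The two sections describe one event.

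**Action required, by pre-exercise glucose (whole mg/dL):**

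| Reading | Section 6.2.1 | Section 7.1 |
|---|---|---|
| Below 100 | 15-30 g carbohydrate snack, timing not stated beyond the pre-exercise check | 15 g glucose, immediately before the test |
| 100-119 | 15-30 g carbohydrate snack | no action stated |
| 120 and above | no action stated | no action stated |

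**Size of the gap.** The triggers differ by 120 − 100 = 20 mg/dL. Below 100 mg/dL the amounts differ by 0 to 30 − 15 = 15 g.

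**Does one rule contain the other?** Not literally. Section 6.2.1 has the higher trigger and an amount at least as large. Section 7.1 is more specific on the meter, the form (glucose) and the timing. A carbohydrate snack at an unspecified time before exercise does not meet the wording of section 7.1 for a subject below 100 mg/dL.

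**Other uses of 120 mg/dL.** Section 6.2.2.4 gives 15-30 g of glucose with protein below 120 after the clamp. Section 7.2 holds T1DM subjects until glucose exceeds 120. Both concern the period after the clamp, so they do not settle the exercise rule. They do show that 120 mg/dL is used as a protective level elsewhere in the protocol.

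**Ages.** The upper limit is 35 in section 7.1 and in section 7.6.1, against 51 in Table 2. Ages 36-51 are eligible but are not covered by the rationale.

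**The case against.** The strongest reply is that the document's structure already favours the safer trigger. Section 6.2.1 is the visit procedure and section 7.1 is a risk narrative, so staff running the visit would be expected to use 120 mg/dL. The test takes about 10 minutes. Both sections then provide food: section 6.2.1 says "the subject will be provided with a meal from the CRC kitchen", and section 7.1 says "Immediately following this, all subjects will be provided with a meal". A reading of 100-119 mg/dL is also well above the levels acted on during the overnight insulin infusion in section 6.2.2.1 (optional dextrose below 75, postponement below 55), although that setting is not exercise. All of this stands and keeps the consequence small. It does not remove the conflict, because the protocol nowhere says that section 6.2.1 prevails.

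Four stronger readings are tempting, and the documents do not support them:

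- A reader might infer that section 7.1 forbids feeding at 100-119 mg/dL. It is silent there and does not prohibit it.
- A reader might infer that pasting the section 6.2.1 rule over section 7.1 is enough. That would lose the glucose form and the immediate timing for subjects below 100 mg/dL.
- A reader might count the HbA1c and BMI ranges in section 7.1 as further weaknesses in its safety argument. Section 7.1 describes "those patients with diabetes will have relatively ideal glycemic control (HbA1c 6.0-8.0"%), and its ceiling is above the 7.5% in Table 2, so it already allows for worse control than is enrolled. The adult BMI ceiling is 28 in both places, and only the lean end differs (20 versus 19).
- A reader might conclude that section 7.1 is simply out of date and that 120 mg/dL therefore governs. The mismatched ranges make an un-updated paragraph plausible, but that is an inference.

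**Conclusion.** The inconsistency is real and minor. It is confined to the 100-119 mg/dL band for whether carbohydrate is called for, and to amount, form and timing below 100 mg/dL. The documents give no distribution of pre-exercise glucose, so the number of subjects affected cannot be estimated, and no harm is shown. Eligibility and the primary comparison of R_d are untouched.

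The age mismatch is also real, but it is a gap in the written rationale and not evidence of high risk at ages 36-51. Table 2 excludes NYHA class II-IV and any antihypertensive or antihyperlipidemic drug, and limits T1DM duration to 20 years. A history and physical examination come before the test. A reader might also infer that a large fraction of participants lie outside the range in section 7.1, because 16 of the 39 eligible whole-year ages for the diabetes groups (36-51 out of 13-51) do. That is a count of ages and not of people, and the documents give no expected age distribution.

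The conclusion assumes only that sections 6.2.1 and 7.1 describe the same test, which their wording establishes.

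**What to change.** State one rule in both sections 6.2.1 and 7.1, combining the timing of section 7.1 with the trigger and amount of section 6.2.1. T1DM subjects take a home-meter capillary reading immediately before exercise. If it is below 120 mg/dL, they take 15-30 g of carbohydrate immediately before the test, and if it is below 100 mg/dL, at least 15 g of that is glucose.

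Secondly, update the ages in sections 7.1 and 7.6.1 to those in Table 2 (T1DM and MODY2 13-51, with controls 18-51 where section 7.1 covers all subjects). In section 7.1, cite the Table 2 exclusions and the pre-test history and examination as the support for ages 36-51.

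The cost is wording edits in three sections. The downside is that some T1DM subjects at 100-119 mg/dL may get a snack that they would not have had under section 7.1. There is no new procedure, no change to eligibility and no effect on the primary analysis.
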